### Pregnancy

UPA is 93-94% effective in preventing pregnancy

LNG-IUS: We hypothesize the LNG-IUS will be as effective as the Copper IUD for EC

If participant reports a positive pregnancy test, we will: 1) invite the participant in for pregnancy testing and transvaginal ultrasound to confirm location and dating of pregnancy. If the LNG-IUS is in place and intrauterine pregnancy is confirmed, we will recommend and complete removal of IUD.

### Pregnancy with IUD

Increased risk of spontaneous abortion

Increased risk of infection in the uterus

Early delivery of fetus if pregnancy continued and IUD left in place

The impact of increased EC access (some forms are now available over-the-counter) on population outcomes and concluded that although use of has EC increased, there has been no demonstrable reduction in unintended pregnancy. By contrast, increased uptake of IUDs in an at-risk population has been shown to dramatically reduce unintended pregnancy and abortion rates. The continued highly effective pregnancy prevention the IUD provides beyond the post-coital period offers a unique opportunity to effect change in the stagnant unintended pregnancy and abortion rates in this country.

Use of the LNG-IUD as an EC method has tremendous public health implications. The device is extremely well liked by users indicating women will continue using it beyond the immediate risk behavior. The numerous non-contraceptive benefits of the LNG-IUD and improved bleeding profile have led to increase uptake when compared to the copper IUD.

Increasing the number of women using IUDs in the post-coital period has the potential to decrease long-term unintended pregnancy and abortion rates in a way that oral regimens have not been able to. Despite improved access to emergency contraception with over the counter availability, rates of unintended pregnancy in the US have not.

## **Study Communications Plan**

1. Washington University School of Medicine LIFE study staff will have regularly scheduled weekly meetings.
  - a. Monthly calls will be scheduled with off-site locations
  - b. Create agenda
    - i. PI needs to approve agenda
    - ii. Email agenda to all members of the LIFE research team the day before the call
  - c. Take minutes during call
    - i. PI needs to approve the minutes
    - ii. Email minutes to all members of the LIFE research team
2. There will be regularly scheduled calls with all study sites. In the early stages of the study the calls and communications may be more frequent.
3. Any adverse events should be reported to the PI immediately.

## **Retention Plan**

As in past contraceptive studies, we will provide incentives to assist with transport and childcare. We plan to closely monitor follow-up rates as well. When participants enroll, we will collect contact information to include the participant's address; home, cell and work phone numbers; email address; and contact information for two alternate contacts as well.

Participants are called 5-weeks post enrollment, six-months post enrollment and 12-months post enrollment for short follow up surveys. They are provided a gift card with each completed survey. Participants are able to schedule calls or complete them at the time of contact. At each survey they are reminded that we will be calling them back in a specific time frame.

Participants are contacted at their preferred contact method which is usually a cell phone. If, after 2 attempted calls they are not reached or do not call back, a call is made to alternate contact numbers for the participant; email contact is then attempted, if the participant has still not responded alternate contacts are called.

## **Study Flow, Clinic Visits, and Duration of Surveys**

### **Initial contact**

#### **Call to screen (5-10 minutes)**

- Participant is introduced to the study
- Participant is screened

If eligible participant is scheduled to enroll as soon as possible

### **Enrollment**

## Clinic visit (30-45 minutes approximately)

- Participant is directed to an enrollment room and given a copy of the *Informed Consent* to read
- Research assistant logs into RedCap, allowing the participant to read the consent paperwork
- Research assistant goes over the consent document allowing the participant to ask questions
- Consents are signed and dated
- Participant is directed to the clinic restroom with instructions given to provide a urine sample for the *Urine Pregnancy Test (UPT)*; and the *self-administered swabs* for chlamydia and gonorrhea testing
- Return to enrollment room and wait for UPT test results to determine eligibility for enrollment
- If participant is not currently pregnant the contact information form, baseline enrollment questionnaire, and clinical enrollment forms are completed
- Randomization to method of Emergency Contraception (EC) is determined
- Participant is directed to clinic waiting room
- Research assistant confers with clinician
- If randomized to oral EC,
  - Participant is given the pills and a cup of water and research assistant observes the participant taking the pill
  - A prescription for refillable oral contraceptive pills is offered
  - Tax forms are filled out and gift card is offered
  - Participant is given UPT to take home
  - Participant is reminded that she will be called for first follow-up in 4-5 weeks
- If randomized to LNG-IUS,
  - Participant is directed to a clinic exam room
  - Clinician performs pelvic exam to determine if there is evidence of cervicitis
  - If no cervicitis is present the LNG-IUS will be inserted by a properly-trained clinicians
  - Tax forms are filled out and a gift card is offered
  - Participant is given UPT to take home
  - Participant is reminded that she will be called for first follow-up in 4-5 weeks

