### **Research Design and Methodology:**

Research design and general methodological approach: We will perform a randomized control trial comparing oral UPA to LNG-IUS for emergency contraception. We will prospectively enroll 532 women experiencing an act of under-protected intercourse within the previous 5 days (120 hours). Participants with a negative pregnancy test, and who meet all inclusion criteria, will be randomized to either an immediate LNG-IUS insertion or oral UPA EC regimen (30mg ulipristal acetate) in a 3:1 ratio. Participants will be provided with a pregnancy test to perform at home and will be called to report the results of the urine pregnancy test 5-6 weeks after insertion. Participants receiving the LNG-IUS will also be return for a brief visit to check LNG-IUS strings. Participants will be contacted via telephone at 6 and 12months post enrollment to complete a follow-up survey. The primary outcome of this study is observed pregnancy rates at 5 weeks and 6 months after enrollment.

Criteria for selection of subjects: Potential participants for this study will be identified in as follows: 1) Women enrolled in the Contraceptive CHOICE Project (CHOICE) who are not currently using a long acting reversible contraceptive (LARC) method and have experienced an act of under-protected intercourse in the previous 5

days; 2) Women presenting, either in person or via telephone contact, to the Barnes Jewish Hospital Women's Health resident OB/GYN clinic who have experienced an act of under-protected intercourse in the previous 5 days; 3) Women identified from an advertising campaign; and

Enrollment: All potential participants receive informed consent and will be directed to make an appointment for consent, randomization, and allocation of method.

Inclusion Criteria:

- Women age 14-45
- Under-protected intercourse within the last five days (120 hours)
- Willingness to accept either IUS intervention or oral EC
- Ability and willingness to follow-up via telephone for results of a urine pregnancy test (UPT)
- Ability and willingness to be contacted by phone for 6 and 12 month follow-up

Exclusion Criteria:

- Positive pregnancy test
- Non-English speaking
- Contraindication to intrauterine contraception or oral UPA
  - Active cervicitis, PID, or recent post-abortal or postpartum infection
  - Undiagnosed abnormal uterine bleeding
  - Known or suspected cervical or endometrial neoplasia

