#### Evaluation/ Follow-Up:

At enrollment all women will undergo a highly sensitive urine pregnancy test as well as self-collected vaginal swab for sexually transmitted disease (STI) testing for *Neisseria gonorrhoeae* and *Chlamydia trachomatis*. Randomization and allocation of emergency contraceptive method will occur immediately following consent. A positive test for an STI will not exclude the patient from participation. All positive *N. gonorrhoeae* or *C. trachomatis* tests will be treated with standard CDC-approved treatment. Partner treatment will also be offered. Women randomly assigned to the LNG-IUS group will be asked to return at 5-6 weeks for a string check. All participants will be provided a urine pregnancy test at enrollment and will be called at 5 weeks post enrollment to obtain results. Participants will then be contacted to complete a follow-up surveys at 6 and 12 months following enrollment.

Measures: Urine pregnancy test results will be documented at 5-6 weeks following method allocation. Negative urine pregnancy tests will be validated by a normal menses after enrollment. Participants testing positive at home will be asked to come into the study site for pregnancy test validation and options counseling. We have studied over 9,000 women attempting to avoid unintended pregnancy in the Contraceptive CHOICE Project. Participants were able and willing to report home pregnancy testing results and/or return for a visit for a sensitive pregnancy test. Any woman who suspects pregnancy, is late for her routine menstrual cycle, or who reports a positive home test will be asked to return to our clinic for pregnancy test validation and options counseling (offered option of continuing the pregnancy or pregnancy termination). *We are using the CONSULT urine pregnancy test which is sensitive to a hcg level of 20mIU/mL with a specificity of >99% (Appendix A).*

Women enrolled in an EC study are clearly motivated to avoid an unintended pregnancy. A negative home pregnancy test and regular menses reliably excludes an on-going pregnancy. Self-report of a negative test and menses will not be validated, as they are acceptable measures to reliably exclude pregnancy. Pregnancy

testing in this protocol has been used for the CHOICE project, with two peer-reviewed publications accepted to the New England Journal of Medicine (Winner B. et al. 2012 & Secura G. et al. 2014)

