### **Data Analysis/Statistical Methods:**

**Preliminary Analysis:** Descriptive analyses will include comparison of the baseline characteristics of participants in the two treatment arms. Continuous variables will be summarized using means, medians, and standard deviations. Categorical variables will be presented as frequencies. Continuous variables that are normally distributed will be analyzed with Students t-test, and nonparametric tests will be used for those that are not normally distributed. Chi-square and Fisher's exact tests will be used to analyze categorical variables.

**Primary Aim:** Observed pregnancies at 5-6 weeks and at 6 months in the LNG-IUD group will be compared to those in the oral UPA group. The analysis population is enrolled women who complete 5-6-week and 6 month follow-up. "Modified" intent to treat analysis will be used. Pregnancies will be presented as frequencies and chi-square tests will be used for analysis. We expect the two groups to be balanced on important confounding variables such as menstrual cycle day at the time of unprotected intercourse. However, if there are significant imbalances, stratified or multivariable analysis will be performed. Pregnancies at 5-6 weeks and 6 months will be compared by intervention arm with Kaplan-Meier estimates, using dating from last menstrual period time. Logistic regression will be used to control for confounding (if necessary) using the dichotomous outcome of pregnancy (yes/no) at each time point.

**Secondary Aim1:** Descriptive analyses will be used to compare demographic characteristics of participants who screen eligible, but decline to participate and those who enroll in the study. Reasons for declining participation will also be collected and qualitatively evaluated for recurrent themes.

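### Active cervicitis is an exclusion criterion but is examined for only after randomisation and only in the LNG-IUS arm, and the plan does not say how women found to have it are analysed

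*Combined protocol and SAP*

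**What the plan says.** The exclusion criteria (Research Design and Methodology) list, under contraindications to either treatment, "Active cervicitis, PID, or recent post-abortal or postpartum infection".

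The enrolment visit (Study Flow, Clinic visit) runs in this order:

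- **Before randomisation.** After consent, a urine sample and self-administered swabs are taken. The woman and staff then "wait for UPT test results to determine eligibility for enrollment". Contact, baseline and clinical enrolment forms follow.
- **Randomisation.** "Randomization to method of Emergency Contraception (EC) is determined".
- **Oral arm.** "Participant is given the pills and a cup of water and research assistant observes the participant taking the pill". No examination is listed.
- **LNG-IUS arm.** "Clinician performs pelvic exam to determine if there is evidence of cervicitis". Then: "If no cervicitis is present the LNG-IUS will be inserted by a properly-trained clinicians". Nothing is said about a woman who does have cervicitis.

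The Evaluation/Follow-Up section agrees that randomisation comes early: "Randomization and allocation of emergency contraceptive method will occur immediately following consent". It adds that a positive gonorrhoea or chlamydia test does not exclude a woman, so the swabs taken in both arms do not apply the cervicitis criterion equally.

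The Primary Aim paragraph of Data Analysis/Statistical Methods limits the analysis to enrolled women who complete the 5-6-week and 6-month follow-up. It calls the approach a modified intention-to-treat analysis and does not define the modification. The Right to Withdraw or Removal section lets investigators remove a participant without her consent, for instance if a condition may jeopardise her welfare or the integrity of the study.

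**The concern.** An eligibility criterion should act on both arms alike, before allocation. Here the examination takes place after allocation, by a clinician who knows it, in one arm. A woman allocated to the LNG-IUS who has cervicitis meets a listed exclusion and has no device. A woman allocated to UPA with the same finding is not examined, so no examination will identify her.

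If the first woman leaves the analysis and the second stays, the analysed groups are no longer the randomised groups. The women at issue are also the ones assigned the device who did not receive it. If their pregnancy risk is higher than that of inserted women, leaving them out makes the observed LNG-IUS rate lower than the rate as randomised, on the trial's primary outcome.

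**Working it through.** **Does any text settle how these women are handled?**

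| Question | What the plan provides |
|---|---|
| Is cervicitis an exclusion? | Yes, for all women |
| Is it examined for before randomisation? | No examination is described; the urine test is the only eligibility test named at the visit |
| Is it examined for in the UPA arm? | No examination is listed |
| What follows if it is found? | No insertion is implied; withdrawal, treatment received and follow-up are not stated |
| Does the analysis population depend on receiving the device? | Not as written; it depends on completing follow-up |
| Is the modification of intention to treat defined? | No |
| Can an investigator remove her? | Yes |

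The handling is therefore open. Dropping these women is permitted, but not stated.

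**The plan's own figure.** Inputs from Power Analysis and Sample Size: 11% (UPA), 2% (LNG-IUS), alpha 0.05 (taken as two-sided), power 90%, 3:1 allocation, about 20% loss. The two-proportion formula with continuity correction gives 108 UPA + 324 LNG-IUS = 432. Dividing by 0.80 gives 135 + 405 = 540, which is 8 (1.5%) above the stated 532. The stated size is reproduced closely enough.

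**Evaluable women after the planned loss.** UPA: 0.80 × 133 = 106.4. LNG-IUS: 0.80 × 399 = 319.2, about 319. Expected LNG-IUS pregnancies at the planned rate: 0.02 × 319 = 6.4.

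**Illustration.** Two inputs are assumed, because the documents give neither: cervicitis prevalence c of 2-10%, and an 11% pregnancy risk if not inserted (the planned UPA rate, borrowed).

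| | c = 2% | c = 10% |
|---|---|---|
| Women affected, 319c | 6.4 | 31.9 |
| Pregnancies among them, 319c × 0.11 | 0.7 | 3.5 |
| As-randomised LNG-IUS rate, 0.02(1 − c) + 0.11c | 2.2% | 2.9% |
| Difference from UPA, 11% minus that rate | 8.8 points | 8.1 points |

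The planned difference is 9.0 points.

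**Direction.** Suppose instead that both arms have a true risk of 11%, and women with cervicitis have RR times the risk of the others (RR assumed). Removing them from one arm leaves a rate of 0.11/(1 − c + c·RR). At c = 10%:

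- RR = 2: 0.11/1.10 = 10.0%, a shift of 1.0 point in favour of the LNG-IUS.
- RR = 0.5: 0.11/0.95 = 11.6%, a shift of 0.6 points against it.

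The sign depends on a quantity that the documents do not contain.

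**Power** (106.4 UPA and 319.2 LNG-IUS women, no continuity correction, against 92.8% with no cervicitis):

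| c | Dropped from the LNG-IUS arm | Kept, at 11% risk |
|---|---|---|
| 1% | 92.7% | 92.2% |
| 3% | 92.6% | 90.9% |
| 5% | 92.4% | 89.5% |
| 10% | 92.0% | 85.4% |

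Dropping the women costs almost no power, so the problem is comparability rather than sample size.

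**The case against.** The strongest reply is that no text removes anyone. Only insertion is made conditional on the examination. The later steps in the same branch (gift card, home pregnancy test, reminder of the first call) carry no such condition, and the Evaluation/Follow-Up section has all participants called at 5 weeks. The analysis population is defined by completing follow-up, so the modification may mean no more than that. Read literally, an uninserted woman who completes both calls is analysed in the LNG-IUS arm. This stands as far as it goes: a reader might infer a planned one-arm exclusion, and the documents do not support that. They also do not rule it out, since she meets a listed exclusion, may be removed by an investigator, and falls under a modified analysis whose modification is not spelled out.

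A reader might also infer that the bias must favour the LNG-IUS. That does not follow either: the documents give no pregnancy risk for women with cervicitis or for uninserted women, and do not say what an uninserted woman receives.

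Finally, the telephone screen and the clinical enrolment forms are not described in detail, so a history-based question asked in both arms is possible. It would narrow the gap, but the examination would still be confined to one arm.

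**Conclusion.** The point holds as a design flaw with an open consequence. A stated eligibility criterion is examined for after randomisation, with allocation known, in one arm only, and the plan does not say how the women it identifies are followed and analysed.

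Neither the size nor the direction of any bias can be derived from the documents. Dropping these women favours the LNG-IUS only if uninserted women have a higher pregnancy risk than inserted women. Under the two assumptions used here (2-10% prevalence, 11% risk without insertion), the LNG-IUS rate reported after dropping them would be 2.0%, against 2.2-2.9% as randomised. That is modest beside the planned contrast of 11% with 2% and would not by itself reverse it. It is still an avoidable departure from the randomised comparison, and worth settling before the analysis.

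**What to change.** - In Data Analysis/Statistical Methods, define the primary population as all randomised women, analysed in their assigned arm whether or not the LNG-IUS was inserted. Name cervicitis, failed insertion and refusal as reasons that do not remove a woman.
- State that uninserted women are followed on the same 5-week, 6-month and 12-month schedule.
- Make an inserted-only analysis secondary.
- Reconcile the cervicitis criterion with the order of steps in Evaluation/Follow-Up and the clinic visit, so that no eligibility criterion removes women after randomisation in one arm only. Which clinical rule to adopt is for the investigators.

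**Cost.** The population and follow-up changes are wording only. Because this population replaces one of completers, the plan must also say how missing pregnancy outcomes are handled. The LNG-IUS rate may be slightly less favourable. Under the assumed 11% risk, power falls from 92.8% to 89.5% at 5% prevalence and 85.4% at 10%. If the reconciliation kept the criterion and applied it by examination before randomisation, every woman would have to be examined; the 532 to be randomised would not change, but more would have to be screened (532/0.95 = 560 at an assumed 5% prevalence, 532/0.90 = 592 at 10%).

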**5-week follow-up**

## Phone call (less than 10 minutes)

- Participant is called and asked if she has time to complete 5-week follow-up or would like to schedule an additional call for a more convenient time
- If scheduling a call,
  - Schedule a call for an appropriate time
- Completing 5-week follow-up,
  - Verify participant's date of birth (DOB)
  - Verify contact information
  - Administer 5-week follow-up in RedCap
  - Ask participant if she has any questions
  - Fill out tax office paperwork
  - Mail gift card
  - Remind participant we will call her for another follow-up in about 5 months

**6-month follow-up**

## Phone call (less than 10 minutes)

- Participant is called and asked if she has time to complete 6-month follow-up or would like to schedule an additional call for a more convenient time
- If scheduling a call,
  - Schedule a call for an appropriate time
- Completing 6-month follow-up,
  - Verify participant's date of birth (DOB)
  - Verify contact information
  - Administer 6-month follow-up in RedCap
  - Ask participant if she has any questions
  - Fill out tax office paperwork
  - Mail gift card
  - Remind participant we will call her for another follow-up in about 6 months

#### 12-month follow-up

##### Phone call (less than 10 minutes)

- Participant is called and asked if she has time to complete 12-month follow-up or would like to schedule an additional call for a more convenient time
- If scheduling a call,
  - Schedule a call for an appropriate time
- Completing 12-month follow-up,
  - Verify participant's date of birth (DOB)
  - Verify contact information
  - Administer 12-month follow-up in RedCap
  - Ask participant if she has any questions
  - Fill out tax office paperwork
  - Mail gift card
  - Thank participant for participating in the LIFE study
